# **Improving balance and physical activity in elderly with Parkinson's disease –effectiveness in a clinical practice of the HiBalance program**

This study is a part of the larger BETA (Balance, Elderly, Training and Activity) study that consists of two parts: Osteoporosis and Parkinson's disease (PD). The long-term goal of the larger BETA study is to reduce the risk of falls in elderly. We predict that increased balance control following training will lead to greater confidence in everyday life, increased levels of physical activity and an improved health related quality of life. The goal is also to establish evidence-based rehabilitation programs for balance and gait function and to further develop and implement an educational curriculum where health care professionals can learn to manage such programs for elderly nationwide.

The BETA-PD study of which [name] is the PI of consists of several parts: method development and laboratory studies, efficacy study and an effectiveness/ implementation study. Here we are applying for the effectiveness and implementation part.

The BETA-PD project aims to translate basic neuroscience into applied research and clinical understanding and implement the evaluation methods and training program into clinical practice. We hypothesize that increased balance control following training will lead to greater confidence in everyday life, increased levels of physical activity and an improved health related quality of life. The addition of physical activity on prescription will further improve the health benefits of this program in the long-term follow-up. With this new concept of balance training, our outcome measurements and educational curriculum, we foresee a paradigm shift in how balance training is applied and evaluated in clinical practice for elderly with balance deficits.

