## **BACKGROUND**

Falls are a major cause of ill-health and may lead to functional impairment, disability, a lower quality of life and fractures among elderly (Kannus, Uusi-Rasi et al. 2005, Madureira, Takayama et al. 2007). Injurious falls and fear of falling are especially common in elderly with Parkinson's disease (PD) (Bloem, Grimbergen et al. 2001). The most is Parkinson's disease (PD). Parkinson's disease is the most common neurodegenerative disorder next to Alzheimer's disease leading to a loss of dopamine producing cells in the basal ganglia and is mainly present around the age of 60 to 85 years of age. The basal ganglia are among the most important central structures for the control of posture and movement. The primary symptoms of PD are tremor, rigidity, bradykinesia and impaired postural stability (balance control) (Nutt, Hammerstad et al. 1992). Many of these symptoms affect balance and walking abilities in everyday tasks (Nutt, Hammerstad et al. 1992, Franzen, Paquette et al. 2009). Postural instability is not just one of the most disabling symptoms of PD it is also one factor that increase the risk of falling, which occurs in 38-68% of the people with PD (Balash, Peretz et al. 2005). Furthermore, elderly with PD have shown reduced levels of physical activity (Fertl, Doppelbauer et al. 1993) and a nine times increased risk of injurious falls, compared with the healthy elderly (Bloem, Grimbergen et al. 2001). Balance and walking impairments are present even in the early stages of PD (Carpinella, Crenna et al. 2007) and have been shown to be associated with restrictions in everyday activities (Tan, McGinley et al. 2011) and reduced quality of life (Ellis, Cavanaugh et al. 2011).

Balance problems may lead to physical inactivity, which in turn leads to increased unsteadiness and a vicious cycle with less mobility, muscle weakness, falls and fractures (King and Horak 2009). Physical activity is today considered a highly potent prevention of and treatment for a large number of conditions and diseases (PAGAC 2008, Ståhle 2010). Approximately 60% of the adult population in the world today does not meet the physical activity recommendations, (Balash, Peretz et al.). However, the level of physical activity in elderly with PD remains unclear. Accelerometer data from

our study show that only 27% of the individuals with mild to moderate Parkinson's disease meet the recommendations of physical activity (Wallén, Franzén et al. Submitted 2014).

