## OBJECTIVES

The specific aims related to Step 3:

1. Describe the utilization and satisfaction regarding balance training and physiotherapy in individuals with PD as well as the treatment characteristics and knowledge regarding PD among physiotherapists in Sweden (surveys).
2. Evaluate the effectiveness of the balance training program regarding gait, balance function, physical activity levels and health related quality of life in clinical settings (case-control study).
3. Conduct a process-evaluation and identify relevant facilitators and barriers for implementation the program into clinical practice (effectiveness-implementation hybrid design).
4. Develop and test educational material for dissemination of the intervention to physiotherapists working with PD and to promote exercise for people with PD

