## CONNECTION TO PREVIOUS PROJECTS / PRELIMINARY RESULTS

During the first years (2011-2013) of the project we have tested the validity and reliability of the measurement methods that we use. For example, we have translated, culturally adapted and tested the validity of the new clinical balance test called, Mini-BEST test, for use in patients with PD. We are now in the process of evaluating its feasibility and reliability. Preliminary results show high concurrent validity, inter- (ICC= 0.775, SEM= 1.78) as well as test-retest reliability (ICC=0.895, SEM = 1.22) in this group of mild to moderate PD. To be able to analyze physical activity measured with accelerometers, methodology studies in PD are also required. We have therefore compared common free-living physical activity parameters assessed with accelerometers and processed with two different filter settings as well as conducted a calibration study in a sample of elderly individuals with PD (Nero et al., accepted Plos One). Furthermore, we have compared self-reported pedometer steps with accelerometer steps in patients with PD and shown that the steps were found to agree poorly with accelerometer steps (Wallen, Dohrn et al. 2013).

We have also conducted a kinematic study in a movement laboratory in which we have investigated turning strategies as well as the effect of levodopa on these strategies in 20 with individuals with PD (ON and OFF their medication) and 20 healthy controls. Preliminary results show an improvement in turning performance due to ant-parkinson medication however no effects on axial coordination (manuscript in preparation).

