### **Effectiveness**

This effectiveness study will be based on the knowledge gained based on the survey and are planned to comprise four to six different clinical settings such as primary care facilities and neurorehabilitation centres. We have already established contacts with primary care and rehabilitation facilities in Stockholm (Stockholms sjukhem, Karolinska universitetssjukhuset, Bromma geriatriken, Stora Sköndal). The academic primary care facilities (Akademiska vårdcentralerna) in Stockholm will also be an interesting partner in the implementation. We expect clinics to join the study in a sequence and are here starting with Stockholms sjukhem, Karolinska universitetssjukhuset and Stora Sköndal. One hundred participants will be recruited through the participating clinics.

100 participants will be recruited from the participating clinics. 50 patients will act as a training group and 50 as a control group. The control group will consist of patients waiting to participate in a training group and will be offered training after a control period of 10 weeks.

The 10-week balance training program (HiBalance) will be performed two or three times per week for one hour each. A pilot study will compare the feasibility, the progression using accelerometers during the session as well as explore barriers and facilitators for performing the training two or three times/week (ethical approval for the pilot Dnr:2015/570-32). The training will be lead by physiotherapists in the clinics. Patient level outcome variables will be adapted to the clinical environment and will be balance performance (Mini-BESTest), gait ability (10 meter walk-test and Timed Up and Go with and without concomitant cognitive and motor tasks), physical activity level and intensity (accelerometers/pedometers), health related quality of life (EQ5D). The tests will be performed by the physiotherapists in the clinic and conducted before and after the training period. As a part of the implementation, we will choose measurements developed and tested in clinical practice.

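### Does leaving the physical activity device and variable unnamed put the physical activity result at risk?

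*Combined protocol and SAP*

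**What the plan says.** Physical activity has a visible place in the protocol. The title begins "Improving balance and physical activity in elderly", and the introduction states: "We hypothesize that increased balance control following training will lead to greater confidence in everyday life, increased levels of physical activity". Aim 2 under Objectives is to evaluate the programme "regarding gait, balance function, physical activity levels and health related quality of life in clinical settings".

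The outcome itself is defined only in the Effectiveness section, as "physical activity level and intensity (accelerometers/pedometers"). The same paragraph says that outcomes will be adapted to the clinical environment, that tests are done before and after the training period, and that "we will choose measurements developed and tested in clinical practice". The paragraph on analysis and sample size names mixed models as the method and the Mini-BESTest as the key outcome. It mentions no activity variable.

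Three other places bear on the point:

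- **Background.** The protocol says that "the level of physical activity in elderly with PD remains unclear" and then cites the group's own accelerometer data, in which "only 27% of the individuals with mild to moderate" disease met activity recommendations.
- **Connection to previous projects.** The group compared two accelerometer filter settings, ran a calibration study, and "compared self-reported pedometer steps with accelerometer steps in patients with PD and shown that the steps were found to agree poorly with accelerometer steps".
- **Study design, methods and workplan.** Accelerometers are listed among the methods of the wider BETA-PD study. Pedometers are not.

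**The concern.** The other patient outcomes in the list each come with a named test or scale: Mini-BESTest, 10 meter walk-test, Timed Up and Go, EQ5D. Physical activity comes with two kinds of device joined by a slash and no variable. Level could mean accelerometer steps, pedometer steps, or the share of patients who reach recommended activity. All three appear elsewhere in the protocol, and the investigators report that two of them agree poorly in this patient group.

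If the choice stayed open until results were in hand, there could be two or three candidate answers for one of the two targets in the title, and a reader could not tell which had been planned. The chance of a false-positive activity finding would then exceed the nominal 5%. Mixing devices across clinics or visits would be a separate problem, because the readings could not be treated as interchangeable.

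**Working it through.** The protocol gives no power, variance or sample size for physical activity, so there is no figure of its own to reproduce. The check has three parts.

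**1. What is fixed, and when**

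| Question | What the protocol offers | Status |
|---|---|---|
| Device | Either of two classes (Effectiveness); accelerometers only (Study design, methods and workplan) | Not stated, but must be chosen before the first baseline test |
| Variable for level | Share meeting recommendations (Background); steps (Connection to previous projects) | Not stated |
| Variable for intensity | None | Not stated |
| Filter setting | Two compared in earlier work | Not stated |
| Mixing or pooling devices | Nothing | Not planned |
| Key outcome | Mini-BESTest | Fixed |

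Measurement takes place before and after training. A patient has to wear something at the first of these, so the device is settled before a post-training value exists. Choosing between a pedometer result and an accelerometer result afterwards would require the same patients to have worn both, and the protocol does not plan that. The three-candidate scenario therefore falls away, because its three readings span both devices. What remains is a choice between variables from one device, for example accelerometer steps against the share meeting recommendations.

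**2. Size of the remaining freedom, if it were misused**

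Inputs: two-sided alpha 0.05, which is an assumption because the protocol gives 0.05 without saying how many sides; two normal test statistics Z1 and Z2 with correlation r; no true effect. The protocol gives no correlation, so r is assumed to lie between 0.3 and 0.9.

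P(at least one p < 0.05) = 1 − P(|Z1| < 1.96 and |Z2| < 1.96)

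Check at r = 0: 1 − 0.95² = 0.0975.

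| r | Two candidates |
|---|---|
| 0.3 | 0.0951 |
| 0.5 | 0.0907 |
| 0.7 | 0.0835 |
| 0.9 | 0.0704 |

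The excess over 5% is thus 2.0 to 4.5 percentage points (7.0 − 5 and 9.5 − 5). Three candidates would give 8.3% to 13.6% over the same range of r, but that case needs both devices on the same patients.

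Under a true effect, two candidates disagree on significance with probability 2 × (power − P(both significant in the favourable direction)). With an assumed power of 80% for each, this is 0.268 at r = 0.3 and 0.100 at r = 0.9. With 50% power it is 0.403 and 0.144.

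These numbers depend only on alpha, r and power. They would be the same for any two unranked outcomes in any trial, so they do not measure a defect particular to this one.

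**3. Whether the poor-agreement finding changes this**

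The earlier comparison was of self-reported pedometer steps with accelerometer steps. It shows that the two devices should not be swapped for each other. It gives no agreement statistic, does not say which device is wrong, and says nothing about two variables from the same accelerometer. It would matter if devices were mixed or if both were worn, and neither is planned. The control group is made up of patients from the same clinics waiting for training, so similar device use in both groups is plausible.

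**The case for a change.** The strongest case for a change is that the gap is undisputed, the outcome is in the title, and closing it would take only a sentence or two. A group that has itself shown the two devices to disagree in Parkinson's disease should say which one counts. Clinics are expected to join one after another, with their own physiotherapists doing the tests, and nothing in the text requires a single device throughout. Listing intensity suggests accelerometers, but then the mention of pedometers has no purpose, and the variable for level is still unstated.

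Much of this stands as description. No section available to us names the device or the variable. It does not follow that the plan is wrong. Asking for one named device and one named variable only asks the sponsor to fill a blank; it supplies no better method, and the sponsor must fill that blank anyway to collect the data. It would not close the matter either, since filter setting, wear time and valid-day rules would remain open. Nor is activity unusual in the list: gait has a walk test plus Timed Up and Go with and without added tasks, several results with no ranking among them. The protocol is also an ethics application for a broad implementation project, and it openly defers the detail of measurement to suit the clinics. That is prospective deferral, and nothing in it suggests selection after the results are seen.

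**Conclusion.** The concern identifies missing detail, and no change to the plan follows. The device question closes by itself before the first baseline test, and the protocol's own pointers (intensity in the outcome list, accelerometers alone among the wider project's methods) lean towards one answer. The choice of variable is one that analysts would ordinarily make and record before looking at outcome data.

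The worst case that remains is a false-positive rate of 7.0% to 9.5% for one non-key outcome. It rests on an assumed correlation of 0.3 to 0.9, a two-sided test, exactly two candidate variables from one device, and a free pick after the results are known, which no section indicates. The Mini-BESTest comparison and the sample size do not depend on the activity measure, so following the plan as written would not give a wrong main result.

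This judgement assumes that devices are not mixed within the trial and that patients do not wear both. If either happened, the poor agreement reported by the investigators would become directly relevant to how the activity data could be used.

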To evaluate the effectiveness of the HiBalance program in clinical settings mixed models will be used. Sample size is based on the key outcome variable (Mini-BESTest) and based on data from the pilot study of the effectiveness study. With a 80% power and an alpha level of 0.05, a minimum of 37 subjects in each group will be required to detect a change of 1 point between groups. The dropout rate was set at 15%, Taken together, to ensure adequate statistical power the sample size for this study would optimally be 50 per group (total n = 80).

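### The sample-size paragraph ends on a total of 80, which contradicts its own 50 per group and the recruitment target of 100, and would miss the stated minimum after dropout

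*Combined protocol and SAP*

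**What the plan says.** All the relevant text is in the Effectiveness section of the combined protocol and SAP.

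- On recruitment: "100 participants will be recruited from the participating clinics", and "50 patients will act as a training group and 50 as a control group". The preceding paragraph gives the same target of one hundred.
- On the calculation, for the Mini-BESTest: "a minimum of 37 subjects in each group will be required to detect a change of 1 point between groups". Power is set at 80% and alpha at 0.05. The calculation is described as "based on data from the pilot study of the effectiveness study"; no standard deviation is printed.
- On attrition: "The dropout rate was set at 15" per cent.
- The conclusion: "the sample size for this study would optimally be 50 per group (total n = 80").

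**The concern.** The concluding sentence gives a per-group figure and a total that cannot both be true of a two-group design. The total is also the only figure in the section at odds with the recruitment plan.

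The figure closes the sample-size justification, so it is where a reader would look to judge whether recruitment was completed. Clinics are expected to join one after another, so someone will have to decide when enrolment is finished. As written, the plan supports two answers: stopping at 80 could be presented as following the protocol, and reaching 100 could be read as over-recruitment. The first matters more, because 80 does not allow for the dropout that the plan itself assumes.

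**Working it through.** **Inputs, all from the Effectiveness section:** minimum 37 per group; difference 1 point; power 80%; alpha 0.05 (sidedness not stated); dropout 15%; target 50 per group; recruitment 100 (50 + 50); bracketed total 80.

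**Step 1. Can 80 be reproduced?**

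| Route | Calculation | Total |
|---|---|---|
| Stated group size | 2 × 50 | 100 |
| Minimum, no dropout allowance | 2 × 37 | 74 |
| Minimum, correct inflation | 37/0.85 = 43.5, so 44 per group | 88 |
| Minimum, shortcut inflation | 37 × 1.15 = 42.6, so 43 per group | 86 |
| Expected completers out of 100 | 100 × 0.85 | 85 |

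None gives 80. The first row agrees with the recruitment target.

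**Step 2. What would 80 deliver on the plan's own inputs?**

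- 80/2 = 40 per group, and 40 × 0.85 = 34 completers, 3 short of 37 in each group.
- Largest dropout that still leaves 37 of 40: 1 − 37/40 = 7.5%, half the planned rate.

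**Step 3. What do 88 and 100 deliver?**

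- 44 × 0.85 = 37.4, which meets 37; 43 × 0.85 = 36.55 does not. So 44 per group is the least that satisfies the inputs.
- 50 × 0.85 = 42.5, above 37. Tolerable dropout is 1 − 37/50 = 26%.

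Steps 1 to 3 need no standard deviation and no choice of test.

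**Step 4. Approximate power (assumption-based).** The plan names mixed models and states neither a standard deviation nor sidedness. I assumed a two-sample t-test for a 1-point difference at alpha 0.05 and solved for the standard deviation that gives 80% power. Because 37 is presumably a rounded-up integer, I solved at exactly 37 per group and, as the other limit, at 36.

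| Test | 80% power reached at | Implied SD | Power at 34 per group | Power at 42 per group |
|---|---|---|---|---|
| Two-sided | 37 | 1.51 | 76.5% | 84.9% |
| Two-sided | 36 | 1.49 | 77.7% | 85.8% |
| One-sided | 37 | 1.71 | 76.9% | 84.3% |
| One-sided | 36 | 1.69 | 77.9% | 85.2% |

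Against the stated 80%, 34 completers per group cost 80 − 77.9 = 2.1 to 80 − 76.5 = 3.5 percentage points. If 37 gives exactly 80%, the loss is 3.1 to 3.5 points.

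**The case against.** The best defence is that this is a slip of the pen with no operational force. The target of 100 is stated twice, the 50/50 split once, and the group size of 50 again in the very sentence that carries the error. Nothing in the plan sets 40 per group, stops recruitment at 80 or uses 80 in an analysis. A careful reader can resolve the conflict on the spot, and the shortfall to 34 completers describes a design that the plan never proposes. The power figures rest on a back-solved standard deviation and a simpler test than the mixed models named. Finally, calling 50 the required 44 plus a margin supplies a rationale that the documents do not give.

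Much of this stands. The error is probably clerical, the harm is conditional, and the power loss is modest and only indicative. How the plan arrived at 50 is indeed not stated, and the 37 cannot be verified without a standard deviation, so 50 can be called adequate only against the plan's own minimum. None of this rescues the number: 80 is wrong as printed, it is the conclusion of the sample-size justification, and the comparison of 34 with 37 rests on the plan's figures alone.

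**Conclusion.** The concern holds. The total of 80 contradicts the group size beside it and the recruitment target, and cannot be derived from the plan's inputs. The rest of the section points to 100 as the intended total.

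The design is not damaged if 100 are recruited: about 42 per group would remain after 15% dropout, above the stated 37. Damage arises only if 80 is taken as the target and dropout exceeds 7.5%. At the planned dropout rate each group would then be 3 short, with a power loss of about 2 to 3.5 percentage points under the t-test assumptions above. The arithmetic conclusion takes the plan's 37 and 15% as given. It should be corrected: the error is certain and sits in a key figure, although its practical consequence is limited.

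**What to change.** Change the bracketed total from 80 to 100, so that it agrees with 50 per group and with the recruitment paragraph. Add the missing step: 37 evaluable per group with 15% dropout requires 44 per group (88 in total), and the recruitment target is 50 per group (100 in total). The sponsor should say in a few words why 50 was chosen over 44, for example as a margin, since the plan does not explain it.

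The cost is a one-line correction. Recruitment of 100 is already planned, so there are no extra patients and no change to the design.
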